6. MILESTONES

7. RATIONALE AND BACKGROUND

Chronic obstructive pulmonary disease (COPD) is a common disease characterized by airway obstruction confirmed by spirometry, often including small airway obstruction, chronic bronchitis, and emphysema (**Barnes 2015**). It is a leading cause of death in the USA, affecting 16 million Americans (National Heart Lung and Blood Institute, USA). The prevalence of COPD in Japan is about 8.6% (**Fukuchi 2004**), costing approximately ¥805.5 billion (US\$6.8 billion) per year (**Nishimura 2004**).

No known medications can reverse COPD, but regular maintenance treatments can help manage symptoms, reduce the frequency of exacerbations, and improve health-related quality of life (**Braido 2016**). Bronchodilators have been the cornerstone of COPD disease management and are prescribed as first-line therapy for patients with COPD. According to the 2017 GOLD guidelines, a long-acting muscarinic antagonist (LAMA) or long-acting beta agonist (LABA) is recommended as the first line treatment in GOLD B, followed by combination therapy LAMA + LABA if the COPD patients are still symptomatic in GOLD D. Several studies have found LAMA+LABA combinations to be more effective than their mono-components and without minimal increase in adverse events. In a review study, Mosely et al. reported that the combination of tiotropium and olodaterol hydrochloride is more effective at improving FEV1 than either of the two agents used alone (**Mosely 2016**). Singh et al., in a phase III trial, found patients receiving tiotropium and olodaterol responded better than those receiving tiotropium monotherapy, and conclude that tiotropium + olodaterol should be considered as a treatment option in patients with moderate COPD who are initiating maintenance therapy (**Singh 2016**). Other clinical trials, such as Tonado 1 and Tonado 2, have also shown that tiotropium/olodaterol fixed-dose combination (FDC) therapy provides significantly improved lung function and quality of life, compared with either therapy used individually in COPD (**Buhl 2015, Ichinose 2016**). In addition, recent clinical trials have found tiotropium/olodaterol FDC therapy significantly improved exercise capacity, and physical activity compared with tiotropium monotherapy. (**Minakata 2019, Ichinose 2018**)

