Patients with uncontrolled COPD experiencing exacerbations may escalate to triple LAMA/LABA/ Inhaled Corticosteroids (ICS) therapy (**Vogelmeier 2017**). According to prior COPD guidelines, ICS can be used for frequent exacerbations, but the most recent GOLD guidelines recommend that ICS only be used for Asthma-COPD-overlap patients (**Vogelmeier 2017**). However, in the DYNAGITO study, the prevalence of LAMA/LABA/ICS (triple therapy) at baseline was 40.8% in moderate to very severe COPD patients in Japan (**Calverley 2018, Ichinose 2018**). ICSs may lead to several minor and major complications. The side effects of ICS treatment can range from weight gain and local side effects, such as pneumonia, oral candidiasis and dysphonia, to adrenal suppression, cataracts, and osteoporosis (**Tariq 2016, Wilkie 2015**). In addition, patients with low blood eosinophil counts may not respond to ICS (**Hizawa 2015**).

Several clinical trials have shown that new LAMA/LABA inhalers could better manage patients, potentially reducing the use of ICS as part and parcel of maintenance therapy in COPD (**Magnussen 2014**). However, the evidence obtained from previous clinical trials is not always reflected in clinical practice, and there is limited research from real world settings

that show LAMA+LABA combination therapy provides more benefit than LAMA monotherapy in Japanese patients with COPD. Therefore, real world evidence from Japanese COPD patients is crucial in addressing this gap in knowledge. It is also essential to understand real world treatment patterns and outcomes, in particular, escalation to triple therapy as a proxy for worsening COPD condition.

Spiolto® Respimat®, a combination of Olodaterol (a LABA) and Tiotropium (a LAMA) (herein referred to as Tio/Olo) was approved in September 2015 in Japan. Spiriva® Respimat®, a Tiotropium (a LAMA) monotherapy (herein referred to as Tio), was approved in October 2004 and widely used in Japan. Both maintenance therapies are available, but real world evidence is lacking if one therapy is superior to the other, and whether it can prolong the duration to triple therapy that includes ICS.

This study aims to evaluate the time to escalation to triple therapy among the Japanese COPD patients newly initiating therapy with Tio or Tio/Olo using real world data.

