9.3.2 Outcomes

9.3.2.1 Primary outcomes

Triple Therapy Use

[figure not shown]
The primary outcome of interest is incident rate of triple therapy initiation (first event per patient) defined as any LAMA/LABA/ICS fixed dose combination or any concurrent use for 30 consecutive days of the following:

- any LAMA/LABA fixed dose combination + any ICS single formulation
- any LAMA single formulation + any LABA/ICS fixed dose combination
- any LAMA single formulation + any LABA single formulation + any ICS single formulation

MDV data has limited information on treatment duration with the days of prescription recorded as 1 day for most patients. Therefore, a days supply of 30 days will be assumed. Although we will require at least 30 days of overlap, the first date of triple therapy overlap will serve as the outcome event date, as corresponds to the initiation of triple therapy. Looking into the future to satisfy the requirement of overlap for at least 30 days has the potential to inflict immortal person-time, but is necessary to differentiate concurrent use when subsequent medication is added (see [Figure 3](#) - example Patient A) from an early sequential prescription fill when subsequent medication is switched to (see [Figure 3](#) - example Patient B).

Figure 3

Illustration of outcome

Censoring

Patients will be censored if they had an occurrence of any of the following: outcome (initiation of triple therapy), death, or end of data. The analysis will use an intention-to-treat censoring approach, which does not account for treatment change. A sensitivity analysis will employ an as-treated censoring approach to further censor upon discontinuation of index therapy or initiation of the other index treatment arm. Thus, events will be assigned to exposure groups according to that patient's original index medication, even if that patient discontinued or crossed over.

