9.7.3 Sensitivity Analyses

1. Less Stringent Qualifying Event Criterion

Instead of defining the event to qualify patients for inclusion based on two prescriptions within 60 days, patients may enter upon only one prescription. While some confidence is lost in whether the patients truly took their index medications, the less stringent qualifying event criterion will allow more patients to be included, increasing statistical power. Furthermore, the possibility of immortal time bias is also mitigated, since the time between prescriptions is no longer present.

2. As-treated Censoring

The analysis will use an as-treated approach for primary, secondary and further endpoint outcomes. In addition to the censoring criteria mentioned for the intention-to-treat approach (outcome, death, or end of data), patients will also be censored after medication discontinuation or switching over to the other arm.

3. Alternative algorithm for COPD

The analysis will use a different set of diagnosis codes for COPD (J43*, J44*) when selecting COPD patients. Compared to the primary analysis, this algorithm omits the diagnostic code for chronic bronchitis (J41*), as this code is commonly used by pulmonologists when prescribing Mucodyne to patients who do not actually have chronic bronchitis. While some true chronic bronchitis patients may be excluded, the selection of patient will increase specificity.

4. Asthma patients with doubt

Asthma patients with doubt are defined as patients with a diagnosis code for asthma and without evidence of any asthma specific treatment (ie., ICS, ICS/LABA). This sensitivity analysis will include patients identified with asthma with doubt.

5. ACOS sensitivity analysis

Patients that have evidence of asthma during the follow-up period will have their data censored on the date of asthma diagnosis during the follow-up period. This will ensure that they contribute information during their COPD disease trajectory up until the time they develop asthma. This approach will mitigate introducing immortal time bias for those patients with ACOS during the follow-up period.

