9.9 LIMITATIONS OF THE RESEARCH METHODS

This study will be conducted using hospital-based health insurance claims following the DPC payment system and is subject to certain limitations. One limitation is that these are based on a large, non-random convenience sample based in Japan, which may contain biases or lack generalizability to other populations. Data also come from a subset of hospitals in Japan, which would lead to failure to record events if patients visit medical centers not included in MDV's data sources (**Tanaka 2015**). Moreover, because healthcare is nationalized in Japan, the notion of enrolment is not applicable, and all patients are assumed to be observable throughout the global date range of the data. However, if a patient's emigration or mortality is not captured, then they would remain in the study despite not truly being eligible for any events, thereby leading underestimations of the risks and rates and possible bias in the hazard ratio if these patients are differentially distributed between the exposed and unexposed groups.

Another limitation of the study is that patients on monotherapy may escalate to double therapy before receiving the triple therapy. The patients starting on double therapy do not have this option. Therefore, patients on monotherapy may take longer to get to triple therapy than the patients on double therapy.

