To assess the primary outcome of triple therapy among those who are not on triple therapy fixed dose combination or filling all the three medications at the same time, an algorithm will be employed to assess the concurrent use (previously described). This algorithm will require us to look into the future to determine the start of the triple therapy and may introduce bias. However, it requires an overlap of only 30 days, and it is unlikely to significantly affect the results.

The primary analysis is being conducted as an Intention to Treat (ITT) approach in which patients are analyzed according to first exposure. However, it is likely that some patients may discontinue their COPD medication or switch over to another cohort. The misclassification of exposure may bias the results. A sensitivity analysis using On Treatment approach will be conducted, which will take into account discontinuation and switching of cohort from one medication to the other.

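### The as-treated analysis censors Tio patients at step-up to Tio/Olo without weighting; adding a weighted version would be a cheap improvement

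*Combined protocol and SAP*

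**What the plan says.** The primary analysis follows patients by first exposure: "The analysis will use an intention-to-treat censoring approach, which does not account for treatment change" (section 9.3.2.1). Section 9.12 accepts that discontinuation and switching may bias that result through exposure misclassification, and gives one response: "A sensitivity analysis using On Treatment approach will be conducted". Section 9.7.3, item 2, states its rule, "patients will also be censored after medication discontinuation or switching over to the other arm", and applies it to primary, secondary and further endpoints. Section 9.3.2.1 words the same rule as a plan to "further censor upon discontinuation of index therapy or initiation of the other index treatment arm". A Tio patient who starts Tio/Olo is therefore censored on that date, and a later triple-therapy event is not counted.

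The only time-to-event model named is Cox regression in the matched cohorts (section 9.7.1.3). No censoring weights are specified, no tabulation of censoring by reason is planned, and neither section 9.9 nor section 9.12 discusses dependent censoring.

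Three other statements bear on the rule. Section 9.9 says that "patients on monotherapy may escalate to double therapy before receiving the triple therapy" and then: "The patients starting on double therapy do not have this option". Section 7 describes LAMA or LABA first, "followed by combination therapy LAMA + LABA if the COPD patients are still symptomatic in GOLD D". Section 7 also treats "escalation to triple therapy as a proxy for worsening COPD condition".

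**The concern.** Switching to the other arm means different things in the two arms. For Tio it is a step up in therapy; for Tio/Olo it is a step down. On the plan's own account, step-up from monotherapy and escalation to triple therapy both follow from disease that is not controlled. If so, the Tio patients removed at step-up have a higher than average risk of the event, and those left under observation look better than the arm as a whole. No matching process operates in the Tio/Olo arm. Matching on baseline covariates cannot correct a dependence that develops during follow-up.

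At stake is how the as-treated result is read. It is the plan's only answer to the misclassification it admits, so readers will take agreement or disagreement with the intention-to-treat result as evidence about robustness. Unweighted, it may not estimate the on-treatment effect.

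**Working it through.** **Plan's own figures.** Section 9.5 assumes 1-year triple-therapy rates of 10% (Tio) and 6% (Tio/Olo), HR 1.73, two-sided alpha 0.05, 90% power and 141 events. Schoenfeld's formula with 1:1 matching gives 4 × (1.960 + 1.282)² / (ln 1.73)² = 4 × 10.51 / 0.3004 = 140, which reproduces the 141. The HR of 1.73 is Tio relative to Tio/Olo. In the direction of section 9.7.1.3 it is 1/1.73 = 0.58. From the two rates, the hazards are −ln 0.90 = 0.1054 and −ln 0.94 = 0.0619, with ratio 0.587. The plan gives no figure for the as-treated analysis.

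**Direction.** Let each patient have a risk multiplier Z (gamma, mean 1, variance θ), Tio event hazard λ·Z with λ = 0.1054, and step-up hazard s·Z in the Tio arm only. Among Tio patients still observed at time t, the mean of Z is 1/(1 + θλt) without step-up and 1/(1 + θ(λ + s)t) when step-up censors. The Tio/Olo arm is unchanged, so at time t the as-treated hazard ratio is inflated by

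(1 + θ(λ + s)t) / (1 + θλt).

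This exceeds 1 whenever θ and s are positive, whatever the true hazard ratio. Example: θ = 1, s = 0.2 per year, t = 1 gives 1.3054/1.1054 = 1.18. If step-up does not depend on Z, s drops out of both means and the factor is 1.

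**Size, under assumptions.** The documents give neither a step-up rate nor its link to risk. Assumed here: s of 0.1, 0.2 or 0.4 per patient-year, θ of 0, 1 or 2, and follow-up of 1 or 2 years. Stepped-up patients take the Tio/Olo hazard. Each simulation used 400,000 patients per arm and an ordinary Cox model. Monte Carlo error is about 0.005: with roughly 40,000 and 24,000 events, √(1/40,000 + 1/24,000) = 0.008 on the log scale, times 0.6.

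| Scenario | HR without step-up | Intention-to-treat | As-treated |
|---|---|---|---|
| Step-up unrelated to risk, all settings | 0.59–0.63 | 0.60–0.71 | 0.59–0.63 |
| Step-up proportional to risk, 1 year | 0.59–0.62 | 0.63–0.70 | 0.63–0.80 |
| Step-up proportional to risk, 2 years | 0.61–0.63 | 0.65–0.75 | 0.66–0.93 |
| One such setting: θ = 1, s = 0.2, 2 years | 0.605 | 0.671 | 0.699 |
| True HR 1.0, proportional, 2 years (two settings) | 1.00–1.01 | 1.00–1.01 | 1.16–1.49 |
| True HR 1.3, proportional, 2 years (two settings) | 1.25–1.28 | 1.13–1.20 | 1.48–1.86 |
| Lower-risk patients leave Tio, θ = 1, s = 0.4, 2 years | 0.610 | 0.664 | 0.541 |

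The two settings for true HRs of 1.0 and 1.3 are θ = 1, s = 0.2 and θ = 2, s = 0.4.

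**Does weighting help?** A further simulation let exacerbations drive step-up, with severity only partly measured. The as-treated HR was 0.62–0.64 unweighted and 0.61–0.62 weighted, against 0.60–0.61 without step-up. With no true effect it was 1.03–1.06 unweighted and 1.01–1.02 weighted. In this milder mechanism the bias is small, and weighting removes part of it.

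**The case against.** **Informativeness is inferred, not shown.** Section 9.9 says only that monotherapy patients may pass through double therapy, and it names no product. Adding a LABA/ICS combination to Tio is itself an event under section 9.3.2.1, so that route stays in the as-treated count. If step-up is unrelated to risk, the as-treated estimate is unbiased and the intention-to-treat estimate is the diluted one. This stands, and it is why the point is conditional.

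**No net direction can be claimed.** The same rule censors at discontinuation in both arms, judged from an assumed supply (30 days for most products) plus a 14-day grace period (section 9.6). The direction of that bias is unknown. This also stands.

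**A reader might infer that the rule always pulls the result toward no effect.** It does not. Risk-related step-up moves the ratio upward, which is toward 1 only when the true ratio is below 1. Section 9.9 itself allows that monotherapy starters may take longer to reach triple therapy, so a ratio above 1 cannot be excluded.

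**A reader might also infer that leaving Tio plus a separate LABA uncensored is an error.** That patient is still on the index drug and has not started the other index arm, so the stated rule is followed. Handling the two step-ups alike would be a different choice of estimand.

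**Weighting has limits.** Section 9.3.3 lists no lung-function or symptom-score covariate, eosinophil counts exist for under 10% of COPD patients, and section 9.4 says hospitals cannot be linked. Weighting can correct only measured dependence. That limits the remedy but does not remove the case for it.

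**Conclusion.** The concern holds in a conditional form. The plan censors Tio patients at a step-up that only monotherapy starters can take and that it links to persistent symptoms, and it makes no adjustment. If step-up tracks the risk of triple therapy, the as-treated Tio/Olo versus Tio ratio is too high: nearer to 1 under the planned benefit, further from 1 if the truth is 1 or more. In the assumed risk-proportional scenarios, 0.59–0.62 becomes 0.63–0.80 over one year, and 0.61–0.63 becomes 0.66–0.93 over two. These ranges show what is possible; they are not forecasts.

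The documents do not support saying that the as-treated result is worse than the intention-to-treat one. Which lies nearer the on-treatment effect depends on the unknown link between step-up and risk. Nor is the primary analysis touched, since it does not censor at switching. This is a low-cost improvement to one of five sensitivity analyses.

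**What to change.** Keep the unweighted as-treated analysis and add a version with stabilised inverse-probability-of-censoring weights. Fit the censoring models by arm, and separately for switching and for discontinuation. Use the baseline covariates plus time-updated exacerbations, oral corticosteroid and antibiotic claims, SABA and SAMA claims, and respiratory admissions.

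Report the number censored by reason and arm. State in section 9.9 that the direction of bias from step-up censoring is conditional as described, that bias from discontinuation censoring has unknown direction, and that weighting corrects only measured dependence: no lung function or symptom scores, and no linkage across hospitals.

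The cost is a change to the plan's wording, somewhat wider confidence intervals for the weighted estimate, and moderate programming. The claims are in the same database, but section 9.3.3 defines covariates at baseline only, so the time-updated versions have to be built.

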9.8 QUALITY CONTROL

The study protocol has been written following the Code of Conduct by the European Network of Centres for Pharmacoepidemiology and Pharmacovigilance (ENCePP) [R15-4870] that provides a set of rules and principles for post-authorization studies with regard to the best practices and

transparency, thereby promoting scientific independence of such studies. The study will be registered to the ENCePP's E-register and the results will also be published on the same site.

The study protocol also follows the key elements of the Guideline for Good Pharmacoepidemiology Practices (GPP) by International Society for Pharmacoepidemiology [R11-4318], and the recent draft Guidance for Industry and FDA Staff "Best Practices for Conducting and Reporting Pharmacoepidemiologic Safety Studies Using Electronic Healthcare Data Sets" [R15-4859]. The guidelines for good pharmacoepidemiology practices (GEP) in non-interventional studies will be respected along with any applicable local laws and regulations. This trial is not in the scope of Good Clinical Practice (GCP) studies.

██████████ will build measures for cohort inclusion, outcomes and covariates. Some of the measure algorithms will be based on those collaboratively developed for another respiratory-related protocol with clinical input from external pulmonology experts (i.e. ICD-10 code lists for comorbidities). Regarding medications, because the health claim coding system in MDV is unique to Japan and not well documented in academic articles, queries based on generic name/brand name will be used to determine the code list for each medication measure.

All measures created, cohorts developed, statistical analyses implemented, and tables completed will undergo quality control review by at least 1 additional analyst or scientist under the supervision of the Principal Scientist. Quality controls include checks for the validity and logical content of codes and checks for missing values and variables. In order to control for potential inconsistencies and errors, all variables will be tabulated. In addition, the distribution of each variable will be examined. Extreme observations with values larger than ± 3 standard deviations (SD) will be examined as potential outliers and consequently excluded from the dataset.

This protocol will be strictly followed in the study. However, measure definitions may undergo modification if determined to be scientifically sensible. All changes to this protocol will be documented in protocol amendments.

